1.2 Scientific Rational: Eradication of HCV in Arizona

HCV related malignancies are among the leading causes of mortality in comparison to death from all other causes in Arizona, especially in the middle-age population (Figure 1). The World Health Organization (WHO) set several recommendations with the goal of eradicating HCV by 2030 and several developed countries have taken the initiative to meet these goals¹⁷. The United States on the other hand is significantly lagging to achieve this target. With the current rate of screening, diagnosis, and treatment, it will take several decades to meet the goals of eradication. There is an urgent need to take aggressive action.

LI-HEPC-AZ V1.0 CONFIDENTIAL According to the Institute of Medicine (IOM), 75-90% of HCV positive individuals in the United are unaware of their infection¹⁰. Current HCV standards encourage screening to only those who are thought to be at risk including injection-drug users, baby boomers, persons with known HCV exposure, HIV infection and patients with signs/symptoms of liver disease^{7, 2}. However, these standards leave millions undiagnosed, hence the increasing trends of HCV^{1, 6}. According to the results of the NHANES questionnaire (Figure 2), the primary reason for lack of treatment is lack of diagnosis¹⁶.

For each new acute HCV case that is reported in the United States, the CDC estimates there are approximately 13.9 actual new HCV cases (reported and unreported)¹⁵. This high ratio (total estimated cases to actual reported cases) is primarily a result of the large proportion of individuals with acute HCV who have asymptomatic or minimally symptomatic infection. Therefore, many may continue to transmit the disease to others but find it unnecessary to seek medical care.

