5.0 Data Management and Analysis

- 5.1 Data Entry and Management
 - >Data will be entered into the electronic data capture system utilized by the Liver Institute PLLC.
 - >Data and results will be entered within a week after they are collected during the mid-study and end-of-study data collection phases.
 - >Data will be de-identified prior to analysis
- 5.2 Data Analysis
 - > A statistician will overlook and conduct final data analysis
 - > Data will be analyzed for trends at the end of the study
 - > Analysis will be completed using IBM SPSS statistics version 24
- 5.3 Results
 - Assuming similar response as obtained for breast cancer or cervical cancer projects, we expect 4% of the targeted population to respond.
 - Based on the prior data, we computed the trend of increase in number of new HCV patients added per year to the pool of diagnosed cohort.
 - According to mapping hep C¹¹, the total number of Antibody screening tests performed in 2016 is 53,580, or 4,465 per month, which is expected to be like current rates of 2019.
 - > We estimate that similar number of subjects will come for self-screening
 - We expected to, at minimum, double the number of screenings to 8,930 tests per month, which will be evaluated after each intervention period as defined in Figure 3. This increase will correlate with the increase in diagnosis rates per 100,000 from 776 to at least 1,552. These numbers will be used as measures of success for the project.
 - Assuming the current rate of 5.2% positive HCV tests holds, we expect at least 464 people to be HCV+ per month from the 8,930 people screened.
 - ➢ From the total number of HCV positive individuals, only 26.1% in Arizona get treatment, which correlates with 120 people per month from the screened population or total of 1440 by the end of the study. Considering there are multiple challenges to treatment and complete eradication, the goal of the study is to promote treatment for those with access to healthcare; expecting to increase treatment rate to about 30%.
 - Statistical data and trends of HCV prevalence over previous years, obtained from the Arizona Department of Public Health, will be compared with the study outcomes to assess the success rate of the study. we expect the number of screened individuals to double and the diagnosis rate to remain at 5.2%. A measure of success is therefore defined as 8,930 or more screening tests performed per month.

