The proposed intervention aims to increase the rate of diagnosed individuals to identify more of the HCV infected population as predicted by Yahia BR, et al (Figure 7)¹⁸. By increasing the number of screened individuals, we predict a 4.0% increase in addition to the current 50% diagnosed and aware.

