7.0 Discussion and Expected Challenges

- Several challenges stand in the way towards complete Hepatitis C eradication. In addition to lack of public awareness leading to low screening percentage, only about 26.1% of the HCV+ population receive treatment.
- During the gap periods of the study the project coordinator will communicate with patients and providers to facilitate the process of treatment. However, several challenges like insurance and access to healthcare might not be inevitable, making it unlikely to increase the treatment rate significantly. On the other hand, the total number is expected to proportionally increase with the number of screened individuals.
- Increasing the public awareness will likely result in a sustained increase in screening rates and gradual improvement in treatment availability and access. Therefore, and through utilizing more efforts the treatment rates can be expected to increase over the upcoming years, moving closer towards our goal of HCV eradication.

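### The 26.1% treatment benchmark is worded as a share of all HCV-positive people but applied to people the study has just diagnosed, so the expected rise to about 30% is not a like-for-like comparison

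*Protocol*

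**What the plan says.** The benchmark appears twice in the protocol. Section 5.3 reads "From the total number of HCV positive individuals, only 26.1% in Arizona get treatment", and Section 7.0 reads "only about 26.1% of the HCV+ population receive treatment". Neither sentence limits the denominator to diagnosed people.

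Section 5.3 then uses the figure as a rate among people found positive by the study. The preceding bullet says "we expect at least 464 people to be HCV+ per month from the 8,930 people screened". The benchmark is converted to a number treated, "which correlates with 120 people per month from the screened population or total of 1440 by the end of the study". The improvement looked for is given as "expecting to increase treatment rate to about 30" per cent.

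Two statements bear on how many infected people are diagnosed. Section 5.3 predicts a gain over the "current 50% diagnosed and aware". Section 1.2 cites a 2010 national report for "75-90% of HCV positive individuals in the United are unaware of their infection".

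Section 4.2 excludes anyone with a current HCV diagnosis, so the study's positives are new diagnoses. Section 2.2 makes the number of patients treated a primary endpoint and the rate of patients undergoing treatment a secondary one.

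**The concern.** A treatment rate over all infected people and a treatment rate over diagnosed people are different quantities. The first counts in its denominator people who cannot be treated because nobody knows they are infected. Section 1.2 itself names missing diagnosis as the main reason for lack of treatment. The study removes that barrier by design, because every positive participant has been tested and told the result. The treated share in that group should therefore exceed a whole-population share even if the linkage system adds nothing.

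At stake is the reading of the treatment result. The third objective in Section 2.1 is to evaluate a central system that links people to care. The 30% is the only figure the protocol gives for an improved treatment rate. If an observed 30% among new diagnoses is set against 26.1% of all infected people, the comparison favours the study and cannot show that linkage helped.

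**Working it through.** **Inputs**

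- Tests per month: 8,930 (Section 5.3)
- Share of tests positive: 5.2% (Section 5.3)
- Treatment benchmark: 26.1%, worded as a share of all HCV-positive people (Sections 5.3 and 7.0)
- Expected improved rate: about 30% (Section 5.3)
- Share diagnosed: 50% (Section 5.3), against 75-90% unaware, i.e. 10-25% aware (Section 1.2)

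**Step 1: reproduce the plan's figures.** Positives per month: 8,930 × 0.052 = 464.4, stated as 464. Treated per month: 464 × 0.261 = 121.1, stated as 120. The benchmark is therefore applied to the study's own positives. At the goal, 464 × 0.30 = 139 would be treated per month.

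**Step 2: put the benchmark on the study's denominator.** Assume that only diagnosed people are treated, and let *d* be the share of infected people who are diagnosed. Then

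rate among diagnosed = 0.261 / *d*

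| Share diagnosed *d* | Implied rate among diagnosed | Equivalent of 464 | 30% minus implied rate |
|---|---|---|---|
| 50% (Section 5.3) | 52.2% | 242 | −22.2 points |
| 60% (assumed) | 43.5% | 202 | −13.5 points |
| 75% (assumed) | 34.8% | 161 | −4.8 points |
| 87% (break-even) | 30.0% | 139 | 0 |
| 100% (26.1% already among diagnosed) | 26.1% | 121 | +3.9 points |

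The break-even is 0.261 / 0.30 = 0.87. On the literal wording, 30% lies below the implied rate whenever fewer than 87% of infected people are diagnosed.

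**Step 3: test against the other awareness figure.** With 25% aware, 0.261 / 0.25 = 104%. With 10% aware, 0.261 / 0.10 = 261%. Both are impossible. As worded, 26.1% treated cannot stand beside 75-90% unaware, and neither can 50% diagnosed and aware, if all three describe the same population.

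**Side note on the total.** 1,440 equals 120 × 12, which is one year. Section 3.1 gives 45 months, and 120 × 45 = 5,400. This is a separate slip, but the same sentence needs revision.

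**The case against.** The strongest objection is that the phrase is ambiguous. The bullet just before the benchmark uses HCV+ for people who test positive, and the benchmark sentence carries on to the screened population. The synopsis also speaks of positive individuals being linked to care, meaning people already identified. Section 7.0 lists 26.1% alongside low screening as a separate barrier and expects treated numbers to grow in proportion to screening. All this fits a rate among identified people. The impossibility in Step 3 also tells against the literal reading. Figure 7 is not reproduced in the text at hand and may state the denominator. This objection stands in part: the intended denominator cannot be settled from the document. It does not remove the point, because the wording in both sections says otherwise, and Section 1.2 uses the same phrase for a group that is mostly undiagnosed.

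A reader might infer that the 30% goal is 22 points below current practice, so that the study could do worse than the status quo and report success. The documents do not support that, for three reasons:

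- The 52.2% divides an Arizona figure by a 50% given alongside a cited US treatment cascade.
- It would be a cumulative rate among everyone ever diagnosed, not uptake among new diagnoses over a set period.
- Section 5.3 names the measure of success as 8,930 or more tests per month, and introduces the 30% only as an expectation.

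A reader might also take 30% as the goal for the primary endpoint. That endpoint is the number treated; the rate is secondary. The 30% sentence also refers to people who can reach health care, a further possible denominator that adds to the need to define it.

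**Conclusion.** The concern holds as a mismatch of denominators. As worded in Sections 5.3 and 7.0, the baseline is a share of all HCV-positive people, while the study outcome is a share of people just diagnosed. On that wording, reaching 30% would not by itself show improvement. The direction holds for any share diagnosed below 87%; the size depends on that share, from about 5 points at 75% to 22 points at the protocol's own 50%. It rests on the literal wording and on treatment requiring diagnosis.

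If the source figure is already a share of diagnosed people, the goal is 3.9 points above it and the fault lies in the wording of the two sections. Either way the text needs correcting, because 26.1% treated of all HCV-positive people is incompatible with 75-90% unaware. The 52% shows how far the denominator matters; it is not a valid benchmark for newly diagnosed participants and should not be written into the protocol.

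**What to change.** - Check the source of 26.1% and state its denominator correctly in Sections 5.3 and 7.0.
- State baseline and target in the same terms: treated divided by PCR-confirmed positive, among newly diagnosed people, over the same follow-up window. Say whether the target is limited to those who can reach health care.
- If no baseline on that footing exists, do not present 30% against 26.1% as an improvement. Report the study's treatment rate descriptively.
- Restate the projections of 120 a month and 1,440 in total to match, including the period that the total covers.
- Reconcile the 50% diagnosed in Section 5.3 with the 75-90% unaware in Section 1.2, or say which population and year each describes.

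The cost is one source check and the revision of a few sentences in Sections 1.2, 5.3 and 7.0. No study procedure changes, provided that the date of PCR confirmation and the start of treatment are recorded for each positive participant so that the common window can be applied.

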1.3 Current Standards: Outreach, Screening, and Therapies

- Currently, there is no standard model of public hepatitis C education and screening promotion. Although approaches like newspaper or media advertisement were used in the past, their benefit remains unknown. On the contrary, there are published reports evaluating the benefit of media campaigns on awareness of breast and cervical cancer screenings. Evaluating the benefit of this project is quite challenging, a meta-analysis revealed short term response of 4% to mass education on improving awareness for mammogram and pelvic examination for breast and cervical cancers, respectively¹⁴. There are no prior studies to estimate the response to HCV screening education in the mass population.
- Current standards encourage HCV screening for individuals considered to be at risk. This includes baby boomers, individuals exposed to infected blood or illicit

drug users. However, these standards do not take into consideration the transmission of disease and other possible causes, leaving millions undiagnosed.

- There are a variety of tests that can detect the presence of Hepatitis C Virus, one of which utilizes anti-HCV ELISA test and is confirmed by HCV PCR. Additional methods include imaging studies and liver biopsies.
- Current standards of treatment include several antiviral medicines that effectively cure the disease in most cases. The course of treatment typically takes 12-24 weeks based on the genotype of disease, extent of liver damage and whether the patient was treated for hepatitis C in the past. In addition to antiviral therapy, complications like cirrhosis and subsequent complications can also be treated using different medical procedures or medicines to prevent risk of liver failure, portal hypertension and liver cancer¹³.
- The Arizona Department of Public Health lags three year on their data compilation and reporting. Most recent data available for review is from 2016.

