2.2 Endpoints

Primary Endpoints:

- Patients screened
- Patients treated

Secondary Endpoints:

- Rate of diagnosed HCV+ individuals
- Rate of patients undergoing treatment
- Increased awareness
- > Identify challenges in terms of identification

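### Section 5.3 judges success partly against past state trends in HCV prevalence, a quantity that matches neither primary endpoint and cannot show whether outreach raised screening or treatment

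*Protocol*

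**What the plan says.** Protocol section 2.2 names two primary endpoints, "Patients screened" and "Patients treated".

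The last bullet of section 5.3 takes state statistical data and "trends of HCV prevalence over previous years, obtained from the Arizona Department of Public Health, will be compared with the study outcomes"; the stated purpose is to judge how successful the study was. The same bullet then expects screening to double with positivity unchanged at 5.2%, and defines a measure of success as at least 8,930 tests per month, joined to what precedes it by the word therefore.

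An earlier bullet of 5.3 gives the baseline behind that pass mark: 53,580 antibody tests in 2016, or 4,465 a month. Its source is the mapping website, not the state department.

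On the state data, section 1.3 says: "The Arizona Department of Public Health lags three year on their data compilation and reporting. Most recent data available for review is from 2016". On undiagnosed infection, section 1.2 says that "75-90% of HCV positive individuals in the United are unaware of their infection" and that about 13.9 new infections occur for each acute case reported.

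**The concern.** A success comparison should set the study's result beside the same quantity measured without the intervention. Here the study produces counts of people tested, diagnosed and treated, and the comparator named is a trend in prevalence. A prevalence figure does not tell the reader how many people would have been tested or treated without outreach.

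A second difficulty arises if the state series is built from reported cases. Such a series reflects both how much infection there is and how hard people look for it. This programme aims to change how hard people look, so a gap between its outcomes and a case-based trend cannot be attributed to infection, to testing effort or to outreach. The protocol also does not say which relation to the state trend would count as success.

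At stake is the interpretation of the final result. A team following the bullet as written could report agreement or disagreement with the state trend and learn nothing from it about either primary endpoint.

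**Working it through.** **1. Reproduce the plan's own figures (section 5.3).**
- Baseline: 53,580 / 12 = 4,465 tests per month, as stated.
- Pass mark: 2 × 4,465 = 8,930 per month, as stated.
- Positives: 8,930 × 0.052 = 464.4 per month (stated 464).
- Treated: 464 × 0.261 = 121.1 per month (stated 120).

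None of these steps uses a prevalence figure. The pass mark is twice a test count from the mapping source, so it does not follow from the state trend.

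**2. Match the comparator to the endpoints.**
- Patients screened: a count of tests. A prevalence trend gives no such count.
- Patients treated: a count of treatments. A prevalence trend gives none either.

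**3. Is the state series case-based?** The protocol does not define it. Section 3.1 uses state rates of hepatitis C per 100,000, section 3.3 describes the same bands as cases per 100,000, and the list of figures calls Figure 4 an average annual rate by county. These point to reported cases. I treat that as likely, not proven.

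**4. If case-based, how far does testing alone move it?** Hold positivity at 5.2%, as 5.3 does.
- Before: 53,580 × 0.052 = 2,786 positives a year.
- After doubling: 107,160 × 0.052 = 5,572 a year.
- Added: 2,786 a year with no change in infection.

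Section 3.2 gives 5,606,808 people aged 15 and over as 80% of the state, which implies 5,606,808 / 0.80 = 7,008,510 in all. The added positives are then 2,786 / 7,008,510 = 39.8 per 100,000, or 2,786 / 5,606,808 = 49.7 per 100,000 aged 15 and over. The medium-prevalence band in 3.1 is 101 to 123 per 100,000. Testing effort alone is therefore worth roughly 32% (39.8 / 123) to 49% (49.7 / 101) of a typical county rate, if every added positive is a newly reported case.

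This shows how sensitive such a rate is to testing. It does not forecast what past state figures will do. The diagnosis rate of 776 per 100,000 in 5.3 is not used here: it lies close to the testing rate (53,580 / 7,008,510 = 764 per 100,000) and is a separate matter.

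**5. Timing.** Section 5.3 treats 2019 as current, and 2019 − 2016 = 3 years, which agrees with the lag in 1.3. A trend that stops in 2016 leaves the years immediately before the study uncovered unless later releases arrive in time.

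**The case against.** The strongest reply is that the bullet contains a usable criterion. At least 8,930 tests per month is a direct measure of the first primary endpoint, so the study does not depend on the prevalence comparison. This stands, and it limits the point. The pass mark does not cover patients treated, however, and does not repair the comparison in the same bullet.

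A second reply is that the sentence opens with state statistical data generally, so the comparator may be wider than prevalence. That is possible, because the contents of the state source are not visible here. The only series the sentence names is prevalence, and the criticism is confined to that series.

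A reader might also infer several stronger points, which the protocol does not support:

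- **That the lag makes the comparison impossible, or leaves state data for only 9 of 45 months (45 − 36 = 9).** The comparator is previous years. A historical comparison can be made despite the lag. The Month 9 limit applies only if someone extends the state series into the study, which 5.3 does not promise.
- **That the study would push the comparator up, so that a working programme reads as worsening disease.** A study cannot alter figures for earlier years. Section 5.3 also lists a rise in diagnosis rates among its measures of success.
- **That the state comparison fails because it is due after every intervention period.** The words "which will be evaluated after each intervention period as defined in Figure 3" belong to the bullet on monthly test numbers. The state comparison carries no such schedule.

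Finally, 1.2 and the closing text of 5.3 differ on how many infected people know their status: 75–90% unaware nationally against 50% diagnosed and aware. Dependence on testing holds at either figure.

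**Conclusion.** The point holds. Section 5.3 commits to assessing success against past trends in HCV prevalence, and that named series measures neither patients screened nor patients treated. If it is case-based, testing effort alone can double positives, from 2,786 to 5,572 a year on the plan's own inputs. The comparison therefore cannot show whether outreach raised screening or treatment. The lag is a secondary weakness: the years just before the start may be missing, and little concurrent state data would exist at study end.

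The conclusion rests on reading the state series as reported cases, which the protocol suggests but does not state, and on the constant 5.2% positivity that 5.3 assumes. The mismatch with the endpoints needs neither assumption. Because a separate pass mark for screening exists, this is a comparison worth correcting; it does not leave the study without any success criterion.

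**What to change.** Replace the prevalence comparison in the last bullet of 5.3 with a like-for-like one:

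- **Screening and diagnosis.** Compare monthly HCV antibody tests and PCR-confirmed positives by county, with and without a study code, from the collaborating laboratory, for about 24 months before the study and throughout it. Counts without a code also show whether free tests merely replace usual ones.
- **Concurrent comparison, only where the rollout allows.** On the months listed in 3.1, medium-prevalence counties are uncontacted to Month 6 and low-prevalence counties to Month 12. In Months 7–12 the uncontacted group is small (490,388 / 5,606,808 = 8.7% of the target population) and was grouped by its lower rate, so it should be compared on change from its own baseline. From Month 13 no county is uncontacted, and the pre-study trend must serve. Section 3.1 also describes the direct-communication period as the first 9 months, which should be reconciled with the listed months first.
- **Treatment.** Compare the proportion of positives treated with the 26.1% that 5.3 already states, defining the denominator and follow-up so that the two figures are comparable.
- **Pass mark and state data.** Keep 8,930 tests per month as a separate criterion with its own stated source, and keep state prevalence as background only.

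The cost is one aggregate data request, assuming the laboratory can supply counts without a study code, and a little more analysis. The limitation is that one laboratory does not represent all testing in the state, and from Month 13 the comparison is before-and-after only.

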2.0 Objectives and Endpoints

2.1 Objectives

- To evaluate the net benefit of an aggressive approach utilizing modern day tools to reach the total population of Arizona at both an individual and population level.
- To evaluate the magnitude of increase in diagnosis rates of Hepatitis C with aggressive outreach to eradicate the disease in the state.
- To evaluate the benefit of utilizing a central system that links identified individuals to a treatment center based upon insurance status.

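### Section 5.3 judges screening by a bare cut of 8,930 tests a month that equals the plan's own expectation, has no stated unit of assessment and does not fit the staged design

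*Protocol*

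**What the plan says.** Section 2.2 lists patients screened as a primary endpoint. Section 5.3 builds the criterion for it in four steps.

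- Baseline: "the total number of Antibody screening tests performed in 2016 is 53,580, or 4,465 per month", taken to hold for 2019.
- Expected addition: "We estimate that similar number of subjects will come for self-screening".
- First statement of the target, worded as a floor: "We expected to, at minimum, double the number of screenings to 8,930 tests per month". The check is to be made once every intervention period has ended, on the schedule of Figure 3.
- Second statement, worded as a point expectation, followed by the criterion: "we expect the number of screened individuals to double and the diagnosis rate to remain at 5.2" per cent, and then "A measure of success is therefore defined as 8,930 or more screening tests performed per month".

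The same section expects 4% of the targeted population to respond. It also names a second success measure, a diagnosis rate rising from 776 to at least 1,552 per 100,000. Section 5.2 says only that data will be analysed for trends at the end.

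Section 3.1 does not reach the whole state at once. It works through high-, medium- and low-prevalence counties in turn, with targeted populations of 391,999, 4,724,421 and 490,388. In the direct-communication phase each group has a six-month window (Months 1–6, 7–12 and 13–18).

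**The concern.** A success cut placed on the value the plan expects, with nothing allowed for variation, leaves the verdict largely to chance when the plan is right. It can also label a large real rise as a miss.

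Two further gaps make the verdict hard to interpret. The text does not say whether 8,930 must be reached in each month, as the mean of each intervention period, or over the study, and it gives no rule for combining repeated evaluations. And one statewide figure is to be checked after periods aimed at county groups whose sizes differ about twelvefold.

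At stake is the main conclusion on screening. Section 2.1 asks for the net benefit of the outreach, and a met/not-met reading of a count does not say how large that benefit was or how precisely it was measured.

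**Working it through.** **Reproducing the plan's figure.** 53,580 / 12 = 4,465 and 2 × 4,465 = 8,930. The threshold reproduces exactly and equals the stated expectation of doubling. The document gives no variance, power or probability of success, so every measure of spread below is an assumption, shown as a range of month-to-month coefficients of variation (CV).

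**One comparison at a true mean of 8,930.** For a single month, P(X ≥ 8,930) is 50.1% under a Poisson count. Under a negative binomial it is 49.4%, 48.7%, 47.4% and 46.0% at CV 5%, 10%, 20% and 30%. For a 30- or 45-month mean under Poisson it is 50.0%.

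**Two-month intervention periods.** The period length is the two months given in Section 3.1; the synopsis describes monthly intervention periods with two-month gaps. For a true monthly mean m, the variance of the two-month mean is m/2 + (CV × m)²/2, with a normal approximation and independent months.

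| True mean | CV 0% | 5% | 10% | 20% |
|---|---|---|---|---|
| 8,930 (doubling) | 50% | 50% | 50% | 50% |
| 8,484 (1.9 × 4,465) | 0% | 7% | 23% | 36% |
| 9,449 | 100% | 94% | 78% | 65% |

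Example, 90% rise at CV 10%: the standard deviation is √(8,484/2 + 848.4²/2) ≈ 603, z = (8,930 − 8,484)/603 ≈ 0.74, and the upper tail is 23%.

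The 9,449 is the section's own 4% response spread evenly over 45 months: 0.04 × 5,606,808 = 224,272; 224,272 / 45 = 4,984; 4,984 + 4,465 = 9,449.

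**Repeated evaluation.** At a constant mean of 8,930 with independent periods, the chance that every period passes is 0.5² = 25% for two and 0.5³ = 12.5% for three. The chance that at least one passes is 75% and 87.5%. The missing combination rule therefore decides the answer.

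**Staged design.** Illustration: 4% of each group responds, evenly over its six-month window, on top of the statewide 4,465.

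- High: 0.04 × 391,999 / 6 = 2,613; total 7,078.
- Medium: 0.04 × 4,724,421 / 6 = 31,496; total 35,961.
- Low: 0.04 × 490,388 / 6 = 3,269; total 7,734.

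At the planned response the expected count falls short of 8,930 in two of the three groups and is about four times the cut in the third. Reaching 8,930 needs 6 × 4,465 = 26,790 responders per window. That is 6.8% of the high group, 0.6% of the medium and 5.5% of the low.

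The window matters. If all responders came in the four active months of the six, the totals would be 15,680/4 + 4,465 = 8,385 (high), 188,977/4 + 4,465 = 51,709 (medium) and 19,616/4 + 4,465 = 9,369 (low). Only the high group would then fall short.

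**The case against.** The strongest reply is that 8,930 is a floor. One sentence says so, and neighbouring figures are also worded as minimums. If the true mean lies above the floor, the chance of passing rises. The section's 4% response gives 65–94% at CV 5–20%. Spread over about 30 active months (assuming fifteen three-month cycles), it gives 224,272/30 + 4,465 = 11,941 a month and about 96% even at CV 20%. This stands as a limit on the 50% figure. It does not remove the problem, because the sentence that derives the criterion, and the estimate of a similar number of self-screeners, treat 8,930 as the expected value.

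A reader might go further in three ways that the document does not support.

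- *A study that performs to plan has a 50% chance of success, or fails half of its periods.* The 50% holds for one comparison at a constant mean of exactly 8,930. The staged groups mean that period results depend mainly on which counties are targeted.
- *The cut discards the size of the increase and contradicts the objectives.* The document calls it one measure of success, names another, and does not forbid reporting the count. The objective on magnitude ("To evaluate the magnitude of increase in diagnosis rates of Hepatitis C with aggressive outreach to eradicate the disease in the state") concerns diagnosis rates, not tests.
- *The same data would have over 99% power, so the cut wastes them.* That power is for detecting any rise above baseline, which is a lower bar than doubling.

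It is also fair to say that the plan claims no power, so no stated figure is wrong, and that intervals and over-dispersion models may sit in an analysis plan not shown here. Figure 3, which is also not shown, may define the periods. The success definition itself, however, is fixed in the Protocol text.

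**Conclusion.** The point holds as a weakness in how the screening criterion is fixed. The cut equals the plan's point expectation, carries no allowance for variation, is worded both as a minimum and as an expectation, and has no stated unit or combination rule.

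A single comparison is met about half the time at a true mean of exactly 8,930, and more often if the mean is higher. A true 90% rise would be scored as a miss in 64–100% of two-month periods. Applied per period, the statewide cut is out of reach in expectation for the high- and low-prevalence groups at a 4% response over six months.

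These sizes rest on assumed CVs, independent months and an even spread of response. The staged result also rests on the six-month window: with response confined to the four active months, only the high-prevalence group falls short. The counts remain usable whatever is done; it is the declared verdict that could mislead.

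**What to change.** In Section 5.3:

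- Make the primary screening result the ratio of monthly tests during the study to the baseline monthly rate, overall and for each intervention period. Give it a 95% confidence interval that allows for over-dispersion and month-to-month correlation, for example from quasi-Poisson or segmented regression.
- Keep 8,930 a month (ratio 2) as a programme target reported beside the estimate. State the period over which it is assessed, and say whether it is a minimum or the expected value.
- Describe a lower confidence limit above 1 only as evidence of an increase over the 2016 baseline. It does not replace the doubling target, since drift since 2016 or a small rise could also produce it.

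The cost is wording and a modest analysis of monthly counts that the 8,930 rule already requires. The document gives the baseline only as one annual total, so monthly baseline counts would have to be obtained to estimate variation before the study. Otherwise the variation must come from the study months alone. The downside is that the headline becomes an estimate with an interval instead of a single pass mark.
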